All the participants will receive a standardized treatment protocol. At the day of bonding, 0.016-inch archwire will be placed for the TuNT group. Eight weeks later it will be replaced by the 0.018-inch archwire for another eight weeks. While, for the CuNT group, 0.014-inch archwire will be placed at the day of bonding and eight weeks later it will be replaced by the 0.018-inch archwire for another eight weeks. Archwires will be tied to the bracket by elastomeric modules. If there is any debonding during treatment, this should be dealt with as an emergency case and re-bonded within 24 hours, otherwise the case will be considered as dropout. Since this study will be performed during the initial phase of treatment, no deviation in the protocol of treatment will be accepted (such as adding additional archwire in the sequence or using power chain). A good-quality alginate impression for the lower arch should be taken pre-treatment and after 4, 8, 12 and 16 weeks and a stone study model is obtained. Periapical X-ray for the mandibular central incisors will be taken pre-treatment and after 16 weeks. The participants will be provided by a visual analog scale (0-10) to record their pain perception during the first week after each wire placement.

Data Collection and Measurements

The following data will be collected and measured during the course of this trial for both groups:

Type of measurement	Pre-treatment T0	After 4 weeks T1	After 8 weeks T2	After 12 weeks T3	After 16 weeks T4
Little's irregularity index	✓	✓	✓	✓	✓
Root resorption using the scoring index that was provided by Malmgren et al. (1982)	✓				✓

Pain perception using visual analog scale (0-10)	24 hours	2 nd day	3 rd day	4 th day	5 th day	6 th day	7 th day
--	----------	---------------------	---------------------	---------------------	---------------------	---------------------	---------------------

Study model which should be free from any discrepancy (such as bubbles) will be used to measure LII using a digital Vernier caliper to calculate the amount of mesial and distal contact displacement from the mesial contact surface of right mandibular canine to that on the other side, to the nearest 0.01 mm. The sum of these measurements represents the amount of LII (**Little, 1975**).

Root resorption will be assessed using the scoring index by **Malmgren et al. (1982)**:

- **Grade 0:** Absence of apical root resorption.
- **Grade 1:** Irregular apical root contour.
- **Grade 2:** Minor apical root resorption, a small area of root loss amounting to less than 2 mm.
- **Grade 3:** Severe apical root resorption from 2 mm to one third of the original root length.
- **Grade 4:** Extreme apical root resorption exceeding one third of the original root length.

The participants will be asked to record their pain perception for the first seven days after placement of archwire using visual analog scale as shown below:

[figure not shown]

Figure 1: Flowchart of data collection and measurement during this RCT.

Timetable

Duty	Expected time
Patient identification and allocation	4 months
Intervention period	4 months
Data collection and analysis	1 month
Writing up the thesis	10 months (starting from the beginning of the trial)
Total expected time to finish	About 10 to 11 months

Stopping Roles

If there is a severe pain in one group that cannot be tolerated by the participants, the study should be terminated.

Budget and Funding

The study is self-funded.

Ethical Approval

The protocol will be submitted to ethics committee.

Data Management and Analysis

Data will be analyzed using the Statistical Package for Social Sciences for Windows, version 25.0 (SPSS Inc., Chicago, Illinois, USA). The following statistical analyses will be used:

Descriptive Statistics

These will include number, frequencies, percentages, mean, median, and standard deviation.

Reliability Statistics

Little's irregularity index: An intraclass correlation coefficient (ICC) will be used to test inter- and intra-examiner reliability of 10 study models measured twice with a four-week interval.

Root resorption: Weighted kappa test will be used to test inter-examiner and intra-examiner reliability of 10 periapical radiographs scored twice with a four-week interval.

Inferential Statistics

Homogeneity of variance between groups will be checked by Levene's test, while normality of data distribution will be checked by Shapiro Wilk test. Assuming that the data are normally distributed due to large sample size (≥ 30) according to the central limit theorem, the following tests will be used:

- *Independent samples t-test:* to test the difference in the amount of crowding between groups.
- *Wilcoxon signed-rank test and Mann-Whitney U test:* to compare the root resorption at T0 and T4 and within each group and between groups (categorical data).
- *Chi-square test:* to compare pain perception between groups.

The significance level will be set as $p < 0.05$

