The aim of this study is to compare the effectiveness of using coaxial tubular superelastic nickel-titanium and copper-nickel-titanium archwires during the initial phase of orthodontic treatment.

Objectives

Primary Objective

To compare the difference in the amount of crowding relief of the mandibular incisors after 4, 8, 12 and 16 weeks from the start of treatment.

Secondary Objectives

1. To compare the amount of orthodontically-induced inflammatory root resorption (OIIRR) in the apical region of mandibular central incisors, after 16 weeks, between the two groups of archwires.
2. To compare the amount of pain perception between the two groups of archwires during the 1st week after each wire placement.

The *null hypothesis* is that “*there is no significant differences in the effectiveness of using coaxial tubular superelastic nickel-titanium and copper nickel-titanium archwires during the initial phase of orthodontic treatment*”.

Methodology

Study design

This will be a multicenter randomized clinical trial.

Settings

Different private clinics and general hospitals will allocate patients for this trial.

Subjects

Participants for this study will include any patient seeking fixed appliance orthodontic treatment according to the below criteria:

Inclusion Criteria:

1. Patients indicated for fixed appliance orthodontic treatment with 5-9 mm crowding of mandibular anterior teeth according to Little's irregularity index (LII).
2. Presence of all the mandibular permanent teeth, except the third molars.
3. Overbite and overjet that do not interfere with bracket placement on mandibular anterior teeth.
4. No history of trauma or root resorption in the mandibular incisors.

Exclusion Criteria:

1. Previous orthodontic treatment.
2. Less than 5 mm of mandibular incisors crowding (LII).
3. Severe crowding which requires treatment by extraction of premolars in the mandibular arch.
4. Blocked-out teeth that cannot be engaged with the aligning archwire.
5. Prior experience of periodontal disease and loss of attachment.

Sample Size

The sample size was calculated to detect a difference of 1.5 mm in the amount of crowding relief between the two treatment groups according to the data obtained from the study by **Nabbat and [name] (2020)**. This revealed that 13 patients in each trial arm will be sufficient to detect this clinical difference (Totals 26 patients). In order to account for dropouts, a total of 30 patients will be calculated.

Intervention

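### The t-test for crowding is justified by a sample of 30 or more, but the plan has about 13 per arm; the justification is wrong and the test is unadjusted, though not invalid

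*Combined protocol and SAP*

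**What the plan says.** Under Inferential Statistics the plan first says that "normality of data distribution will be checked by Shapiro Wilk test". The next sentence makes that check irrelevant: "Assuming that the data are normally distributed due to large sample size (≥ 30) according to the central limit theorem". On that basis it names the independent samples t-test "to test the difference in the amount of crowding between groups". Mann-Whitney is listed only for root resorption, and no alternative is given for crowding if Shapiro-Wilk rejects.

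Under Sample Size the plan states "13 patients in each trial arm will be sufficient to detect this clinical difference (Totals 26 patients" and then "In order to account for dropouts, a total of 30 patients will be calculated". Randomization is simple, with no ratio or blocking stated. The Intervention Protocol adds a route by which patients can be lost: after a debonding that is not repaired in time, "otherwise the case will be considered as dropout". Patients enter "with 5-9 mm crowding of mandibular anterior teeth" on LII, which is a sum of displacements and so cannot fall below zero.

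**The concern.** The sentence makes two errors. It applies a rule of thumb for a single mean to a two-arm comparison and counts both arms together to reach 30. It also treats the central limit theorem as a statement about the data, when it concerns the sampling distribution of a mean.

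At stake is the primary outcome, compared at four visits. Non-normality is plausible late in follow-up, because LII starts at only 5 to 9 mm and is bounded at zero. If Shapiro-Wilk rejects, the analyst must either ignore the result or choose another test after seeing the data. The comparison also takes no account of baseline LII, which is measured at T0 in every patient.

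**Working it through.** **1. The plan's own counts.** 13 × 2 = 26, and 30 − 26 = 4, so the implied dropout allowance is 4/30 = 13.3%. An equal split gives 15 per arm at enrolment and 13 after the allowed losses. The pooled total reaches 30 only if nobody is lost. With independent dropout at rate d, that chance is (1 − d)^30: 0.95^30 = 21% at 5% dropout, and about 1% at 13.3%.

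The figure of 13 cannot be confirmed, because the SD and power are not stated. For a 1.5 mm difference at two-sided 0.05 and 80% power, 13 per arm follows from an SD of 1.26 to 1.30 mm (t-based). I use 1.3 mm below as an assumption.

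**2. Arm sizes under simple randomization.** Assume 1:1 and 30 enrolled, so the arm size is Binomial(30, 0.5).
- P(exactly 15/15) = 14%, so one arm exceeds 15 in 86% of allocations.
- P(smaller arm ≤ 12) = 36%, and P(smaller arm ≤ 10) = 10%.
- No split can put both arms at 30.

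**3. Type I error of the t-test** (100,000 runs per case, nominal 5%).

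| Distribution | 13 v 13 | 10 v 16 |
|---|---|---|
| Normal | 4.9% | 5.0% |
| Gamma, skewness 1 | 5.0% | 4.9% |
| Exponential, skewness 2 | 4.5% | 4.6% |
| Lognormal, log-SD 1 | 3.5% | 3.7% |

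There is no inflation. Shapiro-Wilk at n = 13 detects skewness 1 in only about 18% of samples and exponential data in about 59%, so it is a weak basis for choosing a test.

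**4. t-test against Mann-Whitney, 13 per arm.**
- Lognormal residual LII, halved in one arm, log-SD 0.6/0.8/1.0 (all assumed): power 72/44/27% for the t-test and 76/52/36% for Mann-Whitney.
- Normal data, 1.5 mm, SD about 1.3 mm: about 80% and 76%.
- Floor model, in which baseline is uniform on 5–9 mm, relief is independent of baseline with mean 6 mm and SD 1.3 mm in one arm, and LII is cut off at 0. Here 29% of that arm's values sit at 0 (13% at mean relief 5 mm, 4% at 4 mm). Mean relief in the other arm is 1.5 mm less or 1.5 mm more. I ran 4,000 trials per case:

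| Analysis | 1.5 mm less | 1.5 mm more |
|---|---|---|
| t-test on LII | 53% | 45% |
| Mann-Whitney on LII | 50% | 45% |
| t-test on relief | 75% | 50% |
| Mann-Whitney on relief | 71% | 45% |
| LII adjusted for T0 LII (ANCOVA) | 75% | 63% |

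With no true difference, the rejection rates of all five were between 4% and 5%. The ANCOVA rows use the model-based p-value; the permutation version was not simulated.

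**5. Why adjustment helps.** Let β be the slope of follow-up LII on baseline. The baseline variance is (9 − 5)²/12 = 1.33, and the SD given baseline is 1.3 mm (variance 1.69).
- SD of LII = √(1.33β² + 1.69).
- SD of relief = √(1.33(1 − β)² + 1.69).
- At β = 1 these are 1.74 and 1.30 mm; at β = 0 they are 1.30 and 1.74 mm.
- The noncentrality is 1.5/(SD × √(2/13)): 2.20 for SD 1.74 (power about 56%) and 2.94 for SD 1.30 (about 80%).
- Adjustment works with the 1.3 mm whatever β is. Its simulated power without a floor was about 78%, the small gap from 80% being the cost of the extra parameter.

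**The case against.** The strongest defence is that the sentence is careless but the test is sound. Thirty enrolled does meet the stated threshold as a pooled count, which is probably what was meant. The t-test is robust here, the plan names Shapiro-Wilk, and the median is among the descriptive statistics. Most of this stands, and it limits the point to a wrong justification, a missing fallback and an inefficient comparison.

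A reader might go further in four ways that the documents do not support:
- **That the t-test is invalid.** Its type I error held or was slightly conservative in every case run.
- **That power on the primary outcome is necessarily lost against a rank test.** This appears only under assumed lognormal skew and a halved residual, neither of which comes from the plan. Its stated target is 1.5 mm of relief. In the floor model Mann-Whitney was no better than the t-test.
- **That no arm can exceed 15.** Simple randomization gives no such cap; an arm above 15 simply leaves the other one smaller.
- **That 26 will be the evaluable number.** It is the calculated requirement, not a certain outcome.

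It can also be said that adjustment gains little if the t-test is applied to relief and relief does not depend on baseline. That is right: with the other arm 1.5 mm lower, the floor model gives 75% for both. But the objective and sample size refer to relief while the test is described for crowding, and the plan does not say how strongly follow-up LII tracks baseline. Adjustment avoids having to know.

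**Conclusion.** The concern holds in limited form. The premise of 30 or more is false for a two-arm comparison with 13 planned per arm, and the appeal to the central limit theorem is misapplied. Neither conclusion needs an outside figure.

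The practical effect is modest. Type I error is not at risk in the cases examined. The avoidable loss comes from leaving out baseline LII: up to about 20 points of power (75% against 53% in the floor model), and nothing if the unadjusted test happens to use the better of LII and relief. These sizes rest on an assumed SD of 1.3 mm, a uniform baseline on 5–9 mm and 13 per arm. Power is lower for every method if the effect pushes more values to zero.

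**What to change.** 1. Delete the sentence that infers normality from the sample size.
2. Make the primary analysis the between-arm difference in LII adjusted for T0 LII (ANCOVA), with its 95% CI and a permutation p-value obtained by reassigning the group labels. Relief is T0 LII minus follow-up LII, so the adjusted difference is the same for LII and for relief apart from its sign. This also settles which of the two is being tested.
3. Report Mann-Whitney with the Hodges-Lehmann difference and its 95% CI as the single pre-specified sensitivity analysis for crowding.
4. Keep Shapiro-Wilk as descriptive only, and say that it does not determine the test. Do not add a rule that switches the main test according to how many values lie at the floor; that would make the primary analysis depend on the data.

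The cost is a few sentences, one degree of freedom and a little more analysis work. No extra patients, visits or measurements are needed, because T0 LII is already collected. The change should be made before the data are unmasked.

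### Pain, a 0–10 score taken on seven days after each of two wires, is to be compared only by chi-square, which ignores order and repeated scores; the readable text names no day or summary

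*Combined protocol and SAP*

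**What the plan says.** - **Secondary Objectives:** "To compare the amount of pain perception between the two groups of archwires during the 1st week after each wire placement".
- **Intervention Protocol:** "The participants will be provided by a visual analog scale (0-10) to record their pain perception during the first week after each wire placement". Each arm has two wires, the first at bonding: "Eight weeks later it will be replaced by the 0.018-inch archwire for another eight weeks".
- **Data Collection and Measurements:** the pain table has seven columns, from 24 hours to day 7, and the text says "The participants will be asked to record their pain perception for the first seven days after placement of archwire using visual analog scale". The printed scale and the flowchart are figures that are not in the text available to me.
- **Inferential Statistics:** for pain, only "Chi-square test:* to compare pain perception between groups". For the other ordered outcome the plan uses rank tests: "Wilcoxon signed-rank test and Mann-Whitney U test:* to compare the root resorption at T0 and T4".
- **Descriptive Statistics:** "These will include number, frequencies, percentages, mean, median, and standard deviation". These are not tied to pain and include no confidence interval.
- **Significance level:** "The significance level will be set as" p < 0.05, with no rule for several days or two wires.

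**The concern.** Pearson chi-square asks whether two distributions over unordered categories differ. If one arm all scored 2 and the other all scored 3, the statistic would be the same as if the other arm had all scored 9. The test therefore does not address the amount of pain, which is what the objective asks about. It also needs each score to come from a different patient, while each patient supplies up to 14. It yields a p-value without an estimated difference or an interval.

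The consequence depends on a choice the plan leaves open:

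- **One score per patient:** a real difference is more likely to be missed.
- **Days pooled as if independent:** false positives rise well above 5%.
- **Each day tested separately:** multiplicity arises, as it would with any test.

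With the day, cut-points and use of the 14 scores unstated, all could be settled after the results are seen.

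**Working it through.** **Inputs from the documents.** Scale 0–10, 7 days, 2 wires: 7 × 2 = 14 scores per patient. Sample Size asks for 13 per arm and plans 30 in total, so 30/2 = 15 per arm if split evenly. Alpha is 0.05. The plan's sample size concerns crowding, so there is no pain figure to reproduce.

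**Assumptions (not in the documents).** True difference 2 points; SD 2 or 2.5; arm means centred on 4 or 5; within-patient correlation 0.3, 0.5 or 0.7. Scores are normal, rounded and clipped to 0–10, with 4,000 simulated trials per setting. Chi-square is uncorrected. Bands are 0/1–3/4–6/7–10 (four), 0–3/4–6/7–10 (three) and 0–3/4–10 (two).

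**Step 1: one score per patient, 15 per arm.** Unbanded, 30 scores fall into 2 × 11 = 22 cells, or 30/22 = 1.4 per cell. In simulation at least 98% of expected counts were below 5.

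Benchmark that uses the full scale: SE = SD × √(2/15) and power ≈ Φ(2/SE − 1.96).
- SD 2: SE = 0.730, 2/0.730 = 2.74, Φ(0.78) = 78%.
- SD 2.5: SE = 0.913, 2/0.913 = 2.19, Φ(0.23) = 59%.

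Two bands, SD 2, arm means 3 and 5, cut at 3.5 because of rounding:
- Proportions in the low band: Φ(0.25) = 0.599 and Φ(−0.75) = 0.227; difference 0.372, pooled 0.413.
- SE under no difference: √(2 × 0.413 × 0.587/15) = 0.180. SE under the difference: √((0.599 × 0.401 + 0.227 × 0.773)/15) = 0.166.
- Power ≈ Φ((0.372 − 1.96 × 0.180)/0.166) = Φ(0.12) = 55%.

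Simulated power for 2 points:

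| Test | SD 2 | SD 2.5 |
|---|---|---|
| Chi-square, 11 raw scores | 15–17% | 8–10% |
| Chi-square, four bands | 40–49% | 28–31% |
| Chi-square, two or three bands | 49–56% | 36–40% |
| Mann-Whitney | 72–74% | 53–55% |

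Single-score chi-square false positives are about 2–6%, so the fault here is lost power. At 13 per arm, four bands give 36–42% (SD 2) and 24–27% (SD 2.5), against 64–65% and 48% for Mann-Whitney.

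**Step 2: seven days pooled as independent.** For a mean, pooling understates the variance by the factor 1 + (7 − 1)ρ, which is 2.8, 4.0 and 5.2 at ρ = 0.3, 0.5 and 0.7. Chi-square is affected in the same direction. Simulated false positives are 12–47% with bands and 8–41% without. A real 2-point difference on all days is found 86–99% of the time, so the fault here is false positives. Pooled Mann-Whitney is also inflated (16–39%), so changing the test alone is not enough.

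**Step 3: each day tested separately.** If the days were independent, the chance of at least one false positive per wire would be 1 − 0.95⁷ = 30%. With correlated days it is 18–28% for Mann-Whitney and 18–31% for banded chi-square.

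**Step 4: the replacement.** SD of a seven-day mean = SD × √(ρ + (1 − ρ)/7).
- SD 2, ρ 0.3: 1.26, SE 0.462.
- SD 2.5, ρ 0.7: 2.15, SE 0.787.
- Two points on all days: Φ(2/0.462 − 1.96) = 99% and Φ(2/0.787 − 1.96) = 72%. Simulated Mann-Whitney gives 66–98%, with false positives of 4–6%.
- Two points on days 1–3 only: the mean differs by 2 × 3/7 = 0.86, so Φ(0.86/0.462 − 1.96) = 46% and Φ(0.86/0.787 − 1.96) = 19%. Simulated: 18–46%.
- Mean of days 1–3: simulated power 63–95% for the early-only difference, at a cost of 3–10 points if the difference holds on all days.
- Two wires each at 0.05: at most about 1 − 0.95² = 10% (simulated 6–10%). Holm brings this to 4–5%.

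**The case against.** - **Missing figures.** The scale or flowchart may define bands or show how pain is handled. This stands as a caveat. But the analysis text names none, bands do not deal with repeated scores, and every banded version tried had less power than Mann-Whitney.
- **Pooling is not stated.** The day-by-day table fits separate daily tests equally well, and then each test has one score per patient. This also stands: the pooled figures show one possible reading and are not an error the plan has committed to.
- **The gap can be small.** At 13 per arm with arm means centred on 4, two bands reach 58% (SD 2) and 43% (SD 2.5), against about 65% and 48% for Mann-Whitney. Part of that comes from a false-positive rate of 6–7% caused by discreteness. Centred on 5, two bands fall to about 41% and 34%. The order of the tests never reversed.
- **The remedy is not always better.** For a difference confined to days 1–3, the seven-day mean (18–46%) can fall below day-1 chi-square with two or three bands (36–56%). This is correct, and it is why the window has to be chosen deliberately.
- **Missing interval, and Holm.** The plan gives no confidence interval for any outcome, so that gap is not particular to pain. Adjusting across wires for a secondary outcome is a choice.

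**Conclusion.** The concern holds. Chi-square is the only between-arm test for pain, and it does not suit an ordered score recorded repeatedly in the same patients. That conclusion follows from the text and needs no simulation.

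The sizes depend on the assumed SD, difference, correlation and score distribution. Under those assumptions, with one score per patient and 15 per arm, four-band chi-square loses about 22–34 percentage points of power against Mann-Whitney, and two or three bands lose about 13–25 (smallest and largest gaps between the ranges in the table). Pooling would give false positives of 8–47%.

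This should be fixed. Pain is one of two secondary objectives, and the crowding analysis is not affected.

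**What to change.** Replace the chi-square line with wording such as:

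> For each wire placement, each patient's mean VAS over [days 1–7, or a named early window, fixed before data are seen] will be compared between arms by the Mann-Whitney U test, with the Hodges-Lehmann difference and 95% CI. The two wire comparisons will be Holm-adjusted [or: one wire is named as the main comparison]. Daily scores will be reported descriptively.

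The seven-day mean matches the objective as written; an early window is better if early pain is the main interest.

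An alternative is one prespecified mixed model on the daily scores with arm, day, wire, an arm-by-day term and a patient random effect, naming the term that is the main test. That choice matters. In a one-wire approximation by repeated-measures ANOVA, the arm-by-day test found a days 1–3 difference 69–99% of the time and an all-days difference 5–9%. The arm effect found 18–48% and 68–99% respectively. Testing both unadjusted gave 9–10% false positives.

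The cost is a few lines of wording and the decisions behind them: window, handling of the two wires, and rank test or model. The data stay the same, with no extra patients or visits. Holm lowers the power of the seven-day mean for a 2-point all-days difference on one wire from 66–98% to 54–97% at its first step.
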